18. ANNEX 3. ADDITIONAL INFORMATION

18.1. Core Data Collection

As described in protocol [Section 9](#), questionnaires will be administered via the study website/mobile app, or via outbound calls from the IQVIA call center. Each follow-up method will ask the same questions to elicit the same information irrespective of whether the participant is submitting their data via the study website/mobile app or the IQVIA call center. A study identification number will be assigned to each participant, and for each questionnaire the date of completion will be stored.

Four different questionnaires will be administered to collect data from participants: Baseline (Index Date Dose), Subsequent Dose(s), and Follow-up. An additional questionnaire will be administered by email from the IQVIA Pharmacovigilance Team to confirm patient-reported medically attended safety events of interest with the treating health care provider (HCP). The data to be collected in these questionnaires are detailed below. Closed questions will be used, with limited free text fields used as indicated below. Medical Dictionary for Regulatory Activities (MedDRA) or Drugbank codes will be applied by MedDRA trained coders to any HCP-provided free text prior to analysis.

18.1.1. Baseline questionnaire (index date dose)

- Informed consent
- Age in years (autocalculated based on date of birth, where possible)
- Sex (male/female)
- Ethnicity/Race
- Occupation (sector, e.g. Health & Social Care)
- Medical history
 - Height/Weight
 - Current conditions (*select all that apply*)
 - Asthma
 - Chronic cardiac disease
 - Chronic hematological disease
 - Chronic kidney disease
 - Chronic neurological disorder
 - Chronic obstructive pulmonary disease (COPD)
 - Congestive heart failure
 - Dementia
 - Diabetes
 - HIV/AIDS
 - Immunocompromised (any cause)
 - Solid tumour (localized or metastatic)
 - Leukemia
 - Lymphoma
 - Liver disease
 - Rheumatological disorder
 - Other (specify) (*medDRA coded*)

- How would you rate your health on a scale of 0-10?
- Frailty (Prisma 7 Questions⁶) (*patients age 65+ years only*)
 - Are you more than 85 years? (*this question will be filled from previous responses*)
 - Male? (*this question will be filled from previous responses*)
 - In general, do you have any health problems that require you to limit your activities?
 - Do you need someone to help you on a regular basis?
 - In general, do you have any health problems that require you to stay at home?
 - In case of need can you count on someone close to you?
 - Do you regularly use a stick, walker or wheelchair to get about?
- Any concomitant medication taken within 7 days prior to vaccination (*Drugbank coded*)
- Any prior COVID-19 vaccinations
 - Date of vaccination
 - Dose number
 - Manufacturer
- Any vaccinations (other than the COVID-19 vaccine) in the last 6 months
- Allergies to medication
- Prior infection with test-confirmed SARS-CoV-2 / COVID-19 disease
- Presence of potential active viral disease within previous 3 days prior to vaccination (e.g. fever, symptoms of cold, flu, or other inflammatory/infectious process)
- Pregnancy status (female participants of childbearing potential only)
- Vaccination information (of index dose):
 - Date of vaccination
 - Location (i.e. vaccination center)
 - Vaccine lot number
 - Anatomical site where vaccine was administered (i.e. which arm)
- Contact information for:
 - The participant
 - A secondary contact for the participant [for follow-up purposes only]
 - Primary care physician [for safety follow-up]
- Preferred participant follow-up method – telephone interview or web/app-based questionnaire

18.1.2. Each subsequent COVID-19 vaccine dose questionnaire

- Vaccination information:
 - Manufacturer
 - Date of vaccination
- Pregnancy status (female participants of childbearing potential only)

⁶ https://www.bgs.org.uk/sites/default/files/content/resources/files/2018-05-23/fff_full.pdf

- Any changes in contact information
- Any changes in preferred participant follow-up method

The following additional fields completed if the vaccine received is the Pfizer-BioNTech COVID-19 mRNA vaccine:

- Additional vaccination information:
 - Location (i.e. vaccination center)
 - Vaccine lot number
 - Anatomical site where vaccine was administered
- Any changes in prior submitted medical history
 - Any concomitant medication taken within 7 days prior to vaccination (*Drugbank coded*)
 - Any other vaccinations (other than the COVID-19 vaccine, and other than any previously reported) in the last 6 months
 - Presence of potential active viral disease within previous 3 days prior to vaccination (e.g. fever, symptoms of cold, flu, or other inflammatory/infectious process)

18.1.3. Safety outcome follow-up questionnaire (weekly, monthly, and long-term follow-up, through 24 months following the index date vaccine dose)

In addition to discontinuation data being collected during follow up (discontinuation date, number of vaccine doses received by discontinuation, and discontinuation reason), outcome follow up will include:

- Pregnancy status (female participants of childbearing potential only)
- Have you received any non-routine (unplanned) medical care since your vaccination / last follow-up questionnaire? (*with the below options to be tailored for each country*)
 - Yes – primary care physician / general practitioner
 - Yes – emergency department
 - Yes – hospital (inpatient)
 - Yes – hospital (outpatient)
 - Yes – Intensive Care Unit or High Dependency Unit
 - No

If a participant selects yes to any of the above, they will be asked how many events they need to report, and asked to complete all of the following questions for each event:

- What was the main purpose of your non-routine (unplanned) medical care?
 - I have been diagnosed with this condition in the past, but my symptoms changed or got worse
 - I experienced new symptoms and was diagnosed with this condition for the first time
- Relevant details will be collected:
 - Date of visit
 - Date of end of visit (if applicable)

- Details of HCP (as minimum: name, location, email)
- Were you diagnosed with any of the following (*closed question for medically attended safety events of interest as listed in protocol Section 9.3.1*)
- Were you seeking care for any of the following symptoms (*closed question for reactogenicity as listed as part of the medically attended safety events of interest in protocol Section 9.3.1 (note: reactogenicity questions will only be solicited at week 1 post each dose)*)
- Did you receive any other diagnosis from your health care provider? (*medDRA coded*)
- For each event/diagnosis, select an outcome:
 - Recovered
 - Recovered with some lasting effects
 - Getting better
 - Condition/symptom continuing
 - Unknown
- Change in pregnancy status (female participants of childbearing potential only) since your vaccination / last follow-up questionnaire
- Any changes in contact information since your vaccination / last follow-up questionnaire
- Any changes in preferred participant follow-up method since your vaccination / last follow-up questionnaire

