If the participant fails to submit follow-up data and is non-responsive to follow-up reminders or telephone calls, follow-up with a secondary contact and the participant’s primary care provider will be attempted.

090177e1991e3913\Approved\Approved On: 18-Jan-2022 22:29 (GMT)

Outcome Data Collection and Review

Outcomes to be collected in this study will include medically attended safety events of interest that are based on:

- Participant self-report during the specified follow-up schedule, or
- Spontaneous participant self-report outside of the specified follow-up schedule.

All medically attended safety events of interest will be captured on the appropriate eCRFs as designated by Pfizer.

Participant reported events of interest will be actively followed up for validation through direct follow-up with the treating HCP or healthcare facility and/or review of medical record documentation.

Scientific Steering Committee

IQVIA will assemble a team of independent external advisors for a Scientific Steering Committee (SciSC) and will develop the charter for the SciSC with input from Pfizer. Global experts will be included with an estimated 3-5 members, who will participate in regular teleconferences over the study period, with additional conferences to be convened as required. The role of the SciSC is to provide guidance on study design issues, ensure safeguards of the interests of the participants, and evaluate the results of interim and final analyses.

Study Size:

This study will aim for up to 10,000 Pfizer-BioNTech COVID-19 mRNA vaccine recipients with 2 years of follow-up data to give adequate precision of the estimated incidence rate, using a 95% confidence level to estimate the incidence of medically attended safety events of interest and other clinically significant events. In order to reach this estimated sample size of vaccine recipients with complete data, 13,334 participants will be targeted for enrolment, assuming a 25% dropout rate over the 2-year follow-up period.

Data Analysis:

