Data collection will be performed at baseline (Pfizer-BioNTech COVID-19 mRNA vaccine dose received at index date), and at weeks 1, 2, 4, 6, 8, 12 and every three months thereafter, through 24 months following index date (or until the occurrence of death, withdrawal of consent, loss to follow-up, or end of study period, whichever occurs first). In addition, data will be collected on any subsequent vaccine doses received during the study period. If a participant receives a subsequent Pfizer-BioNTech COVID-19 mRNA vaccine dose during the study period, the data collection schedule will reset based on the reported date of subsequent vaccine dose, with data collected at weeks 1, 2, 4, 6, 8, 12 and every three months thereafter from the reported date of subsequent vaccine dose only. If a participant receives another COVID-19 vaccine (**not** the Pfizer-BioNTech COVID-19 mRNA vaccine) dose during the study period, the data collection schedule will not reset, but the participant will remain in the study and the follow-up schedule will continue based on the previous Pfizer-BioNTech COVID-19 mRNA vaccine date. The observation period will not be extended if subsequent doses are received; the observation period will remain at 24 months following baseline (vaccination dose received at index date), or until the occurrence of death, withdrawal of consent, loss to follow-up, or end of study period, whichever occurs first.

An overview of the data collection schedule is shown in [Figure 1](#).

Figure 1. Data Collection Schedule

¹ Index Dose can be Dose 1, Dose 2 or Booster/Additional Dose

Participants may also report medically attended safety events of interest at any time outside of regular survey follow-up, via the participant portal within the study website or mobile app, or to the IQVIA call center.

Participant reported medically attended safety events of interest will be confirmed by the treating HCPs or through medical record documentation if needed to validate or establish the diagnosis associated with the event and validate the occurrence of a safety event of interest, or other clinically significant events. This process is further detailed in [Section 10](#).

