9.2. Setting

This primary data collection study will aim for up to 10,000 vaccine recipients with 2 years of follow-up data. In order to reach this estimated sample size of vaccine recipients with complete data, 13,334 participants will be targeted for enrolment, assuming a 25% dropout rate over the 2-year follow-up period. The study will be conducted in Germany, Italy and Spain in a total of approximately 20 centers. Other countries may be included in addition to, or as a replacement, for one or more of these countries, as required to fulfill study objectives.

It is anticipated that participants will be enrolled from settings based upon the regional availability and distribution of vaccine according to national or regional COVID-19 preparedness plans and may include physician offices, hospitals, pharmacies, and/or vaccination centers. Site selection criteria will include the projected availability of eligible participants in the enrolment period and the availability of physician (and other site staff) time to complete brief baseline case report forms (CRFs) where required. Selection criteria and basic site information (e.g. site size, site type) will be collected via a site qualification survey.

Limited inclusion/exclusion criteria will be applied in this study, to ensure comprehensive capture of individuals receiving the Pfizer-BioNTech COVID-19 mRNA vaccine in real-world settings.

Participants will be considered enrolled if they meet the inclusion/exclusion criteria below, have provided informed consent (as required per local regulations), and have reported the date of Pfizer-BioNTech COVID-19 mRNA vaccination at baseline.

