	Subacute thyroiditis
Cardiac	Myocarditis
	Pericarditis
	Acute myocardial infarction
	Microangiopathy
	Heart failure
	Stress cardiomyopathy
	Coronary artery disease arrhythmia
Hematologic	Thrombocytopenia
	Disseminated intravascular coagulation
	Coagulation disorder (includes thrombotic disorders, bleeding disorders)
Other	Death
	Narcolepsy and cataplexy
	Non-anaphylactic allergic reactions
	Reactogenicity 
 • Injection site reaction (redness, warmth, pain, itch, hematoma, swelling, induration) • Fever/feverishness • Shivering/chills • Headache • Vomiting and Diarrhoea • Myalgia/muscle pain • Arthralgia/joint pain • Malaise • Fatigue

a. The medically attended safety events of interest in this study are based on the adverse events of special interest (AESI) defined by ACCESS as well as the Coalition for Epidemic Preparedness (CEPI)-funded Safety Platform for Emergency vACCines (SPEAC) working with the Brighton Collaboration. Additional medically attended safety events of interest may be identified as information emerges about events potentially related to vaccines. Details on risk windows for events will be detailed in the SAP.

Table 2. Medically attended safety events of interest^a

Body System	Safety Event
-------------	--------------

* Hospitalized manifestations only.

** All hospitalized COVID-19 disease will be assessed for vaccine-associated enhanced disease.

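### The scheduled follow-up form has no answer option for care given only at a vaccination center or pharmacy, so allergic reactions treated and ended on site may be missed or left to spontaneous report.

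*Protocol*

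**What the plan says.** **The gate.** Section 18.1.3 asks "Have you received any non-routine (unplanned) medical care since your vaccination / last follow-up questionnaire". The positive answers are general practitioner, emergency department, inpatient, outpatient, and intensive or high-dependency care. The only other answer is *No*. The list carries the note "with the below options to be tailored for each country".

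**The skip.** "If a participant selects yes to any of the above, they will be asked how many events they need to report". The diagnosis item, "Were you diagnosed with any of the following", and the item on any other diagnosis come after this step.

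**The settings.** Section 9.2 says that enrolment settings "may include physician offices, hospitals, pharmacies, and/or vaccination centers".

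**The outcomes.** Table 2 in Section 9.3.1 lists anaphylaxis and "Non-anaphylactic allergic reactions". Annex 4 names both as suitable for SCRI analysis.

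**The second route.** Section 9.1 states: "Participants may also report medically attended safety events of interest at any time outside of regular survey follow-up". The Abstract lists "Spontaneous participant self-report outside of the specified follow-up schedule" as an outcome source beside scheduled self-report.

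**The concern.** Immediate allergic reactions are the listed events most likely to begin, and sometimes to end, where the vaccine was given. A participant treated by staff at a vaccination center or pharmacy and then sent home finds no positive answer that describes this care. The nearest available answer is *No*, and that closes the form before the diagnosis list appears.

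The cases at risk are those closest to the dose. Any loss goes in one direction, towards fewer events after vaccination. A statistical analysis plan cannot repair it, because the data would never have been collected.

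**Working it through.** The point concerns questionnaire routing. The protocol states no figure to reproduce, so the check sets the sections side by side.

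**1. Which settings have a matching answer?**

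| Setting (Section 9.2) | Matching positive answer in 18.1.3 |
|---|---|
| Physician office | General practitioner |
| Hospital | Hospital inpatient or outpatient, emergency department |
| Pharmacy | None |
| Vaccination center | None |

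A reaction that starts at a pharmacy or center and is passed on to a general practitioner, emergency department or hospital also fits. What remains is care that begins and ends on site in the last two settings.

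**2. Does another scheduled form ask?**

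- Baseline questionnaire (18.1.1): no event or immediate-reaction item.
- Subsequent-dose questionnaire (18.1.2): none.
- Table 3: safety events are marked only in the two follow-up columns, not at baseline or at a subsequent dose.
- Telephone follow-up: Section 18.1 says that every follow-up method asks the same questions, so the same gate applies.

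**3. Does the time frame cover the day of the dose?** The form asks about the period since vaccination, so it does. Section 9.3.1 instead starts event collection at enrolment, which Section 9.2.1 allows up to 5 days after the dose. Section 9.7 counts time at risk from the dose. The form and Section 9.7 agree; Section 9.3.1 does not, and the disagreement falls on exactly these early reactions.

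**4. Which way would a loss act?** Let N be the true count of an event in the period analysed, m the number lost, PT the person-time, and E the expected count from background rates.

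- Incidence: (N − m)/PT instead of N/PT.
- OE ratio: (N − m)/E instead of N/E. E comes from outside sources and is unaffected by the form.
- SCRI: the incidence rate ratio is (n_r/L_r)/(n_c/L_c), with n the cases and L the length of the risk (r) and control (c) intervals. If the risk interval includes the day of the dose (an assumption, since the protocol leaves the windows to the statistical analysis plan), on-site losses come out of n_r only. The ratio is then multiplied by (n_r − m)/n_r. Self-control does not cancel this.

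All three move downward when m > 0.

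**5. How large is m?** The protocol gives neither the share of participants vaccinated at pharmacies or centers, nor the share of reactions handled wholly on site, nor the share of those later reported spontaneously. The size cannot be derived.

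**The case against.** The case on the other side has five parts.

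- **Spontaneous reporting is an accepted outcome source.** It is open at any time by portal, app or call center, with no stated filter on where care was given. This stands, and it rules out the inference a reader might draw that on-site reactions are simply not captured. But the route is unprompted, and it relies on a participant volunteering an event after the form has led to *No*.
- **The answer list is not final.** Country tailoring could add the vaccination site. It could, but nothing commits any country to do so.
- **The gate question itself covers any unplanned care since vaccination**, so *No* would be untrue for someone treated on site. This is correct, but no positive answer is true either.
- **Vaccinating staff may act as designee** under the note to Table 1, and so may report events. This is permitted, but no form completed at the dose asks them about a reaction.
- **The effect on OE and SCRI results may be slight in practice.** The Abstract reserves OE comparison for events with enough cases, and Section 9.7 does the same for SCRI. As an illustration, assume a 2-day window: 13,334 index doses × 2/365.25 ≈ 73 person-years. At three of the illustrative rates in Table 4 (1, 5 and 10 per 10,000 person-years), about 0.007, 0.04 and 0.07 cases are expected. Neither comparison may be run at such counts. This stands for OE and SCRI, but not for the incidence rate, which is the primary objective; with so few cases, each one lost is a large relative change.

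**Conclusion.** The gap is real but limited. As Annex 3 is written, the scheduled form offers no answer for care given and completed by staff at a vaccination center or pharmacy, and no other scheduled form asks. Anaphylaxis and non-anaphylactic allergic reactions handled that way may be missed or left to spontaneous report. Any resulting bias in incidence, and in any OE or SCRI estimate, is downward. For SCRI this assumes that the risk interval includes the day of the dose.

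The size is unknown and should not be guessed. A reader might be tempted to take an assumed share q of immediate reactions lost on site and multiply the whole OE ratio by (1 − q). The protocol does not support this. It gives no value for q, and under Section 9.7 the expected count is of coincidental cases, which have no reason to cluster at the vaccination site. If only excess cases were lost, a true ratio of 1 + x would fall to 1 + (1 − q)x and would stay at or above 1. An apparent protective effect would require coincidental cases to be lost too.

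This is a cheap improvement to the instrument, not a flaw that undermines the study.

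**What to change.** 1. In every country version of the opening question in Section 18.1.3, add *Yes - treated by staff at the vaccination site* and *Yes - other*. Either answer should open the event questions.
2. State in Section 9.3.1 that care given by staff at the vaccination site counts as medically attended.
3. Reconcile the start of event collection: Section 9.3.1 says enrolment, while the form and the time at risk in Section 9.7 run from the vaccination.

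Optional: add one ungated item on immediate reactions to the baseline and subsequent-dose forms, with matching marks in Table 3. Step 1 is enough to close the gap, because the week 1 form already looks back to the dose.

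The cost is two answer options, a small change to the app and telephone script, and two text edits. The downside is a few more minor reactions to validate.

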The study period is 30 months. Each participant will be followed from baseline (vaccination dose received at index date, where index date is defined as the date of Pfizer-BioNTech COVID-19 mRNA vaccine dose received within the 5 days prior to enrolment, regardless of dose number) until death, withdrawal of consent, loss to follow-up, 24 months or end of study period, whichever occurs first.

Data will be collected at baseline directly from the participants receiving the vaccine and/or their designee; this may include a health care provider (HCP) or study staff at the site administering the vaccine.

This study will collect information on all reported occurrences of the medically attended safety events of interest, which is based on the AESI lists specified by ACCESS and SPEAC/Brighton Collaboration, for which the participant sought medical care during the study period. Participants will choose their preferred method for submitting follow-up data:

- Completing questionnaires via a participant portal within the study website or mobile app, or
- Telephone interview via outbound calls from the IQVIA call center.

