9. RESEARCH METHODS

9.1. Study design

This is a prospective, observational, multi-center, non-interventional PASS conducted to evaluate safety of study participants receiving the Pfizer-BioNTech COVID-19 mRNA vaccine using a combination of primary data collection and secondary data analysis. This study will not provide or make recommendations on any vaccine use. Participants will be invited to enroll and consented in the study after the decision has been made to administer the vaccine, and participation in this study will not change or influence a participant's standard of care in any way. There are no protocol-mandated visits or procedures associated with the study. The study period is 30 months. Each participant will be followed from baseline (vaccination dose received at index date, where index date is defined as the date of Pfizer-BioNTech COVID-19 mRNA vaccine dose received within the 5 days prior to enrolment, regardless of dose number) until death, withdrawal of consent, loss to follow-up, 24 months or end of study period, whichever occurs first.

Data will be collected at baseline directly from the participants receiving the vaccine and/or their designee; this may include a health care provider (HCP) or study staff at the site administering the vaccine. Follow-up data on medically attended safety events of interest will be collected directly from persons receiving the vaccine.

[figure not shown]
This study will collect information on all reported occurrences of the medically attended safety events of interest, which is based on the AESI lists specified by ACCESSS and SPEAC/Brighton Collaboration, for which the participant sought medical care during the study period. Participants will choose their preferred method for submitting follow-up data:

- Completing questionnaires via a participant portal within the study website or mobile app, or
- Telephone interview via outbound calls from the IQVIA call center.

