9.5. Study size

The primary objective of this study is to quantify the incidence of medically attended safety events of interest by estimating their incidence rates per 10,000 person-years, calculated as the number of participants experiencing the event after receiving a dose of the Pfizer-BioNTech COVID-19 mRNA vaccine during the person-time at risk (numerator) divided by the total person-time at risk (denominator).

The target for enrolment will be approximately 13,334 participants (vaccine recipients). Table 4 provides illustrative examples of expected margin of error ([width of confidence interval/2]) for different incidence rates per 10,000 person-years. The margin of error was calculated for a range of attrition rates (25%, 40%, and 55%) for illustrative purposes.

Table 4. Margin Of Error Scenarios For Targeted Sample Size And Different Incidence Rates Over A 24-Month Follow-Up Period

Target n	Attrition rate assumption	Expected n who complete 24 months follow-up	Incidence rate (per 10,000 person-years)	95% Confidence intervals (exact) according to different incidence scenarios	Margin of error
13,334	25%	10,000	1	[0, 3]	1.5
			5	[3, 9]	3.0
			10	[6, 15]	4.5
			50	[41, 60]	9.5
			250	[230, 271]	20.5
			500	[472, 530]	29.0
			2500	[2436, 2565]	64.5
			5000	[4910, 5092]	91.0
	40%	8,000	1	[0, 4]	2.0
			5	[2, 10]	4.0

Table 4. Margin Of Error Scenarios For Targeted Sample Size And Different Incidence Rates Over A 24-Month Follow-Up Period

Target n	Attrition rate assumption	Expected n who complete 24 months follow-up	Incidence rate (per 10,000 person-years)	95% Confidence intervals (exact) according to different incidence scenarios	Margin of error
			10	[5, 17]	6.0
			50	[39, 64]	12.5
			250	[223, 279]	28.0
			500	[462, 540]	39.0
			2500	[2414, 2588]	87.0
			5000	[4878, 5124]	123.0
	55%	6,000	1	[0, 6]	3.0
			5	[1, 12]	5.5
			10	[5, 20]	7.5
			50	[37, 68]	15.5
			250	[218, 286]	34.0
			500	[454, 549]	47.5
			2500	[2396, 2607]	105.5
			5000	[4853, 5151]	149.0

The 95% confidence intervals are derived using the (exact) Clopper and Pearson method.

Calculations were done in R Version 4.0.2.

Further analyses described in [Section 9.7](#) for secondary endpoints will be exploratory in nature and will not involve formal hypothesis testing. The statistical analysis plan (SAP) will expand the statistical methods mentioned in [Section 9.7](#) of this protocol.

090177e1991e3913\Approved\Approved On: 18-Jan-2022 22:29 (GMT)

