Time at risk will be assessed from the Pfizer-BioNTech COVID-19 mRNA vaccine dose until the subsequent follow-up time point or until the next Pfizer-BioNTech COVID-19 mRNA vaccine dose received, death, withdrawal of consent, loss to follow-up, 24 months or end of study period, whichever occurs first. Sensitivity analysis may be conducted with censoring at any COVID-19 vaccine dose received.

All cases of reported laboratory confirmed COVID-19 in the study population will be described by the Brighton Collaboration “Vaccine-associated Enhanced Disease” Working Group case definitions for COVID-19 VAED.

Counts of newly reported medically attended safety events of interest and counts of vaccinated participants will be summarized as per the intervals above. Counts will be summarized by whether medical validation of the event was possible, or not.

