To answer the first secondary objective, the observed rate of events will be compared with expected rates using the Observed to Expected (OE) analysis approach (6). The core principle of OE analysis is to estimate the expected number of coincidental cases of medically attended safety events of interest, under the assumption of no association with the vaccine. Expected numbers are then compared with the number of cases actually reported in vaccine recipients. The expected background incidence rate of a particular safety event of interest is the number of new cases occurring naturally in the population, expressed in person-time. The comparison of OE number of medically attended safety events of interest will be expressed as the ratio of the observed over the expected: an OE ratio equal to 1 means that the observed number of cases equals the expected number of cases, whereas an OE ratio greater than 1 signals an excess of risk in the vaccinated population. The statistical uncertainty of the OE analysis will often be driven by the observed number of cases, which are often rare events. To deal with this statistical uncertainty, a 95% Poisson exact confidence interval (95% CI) will be calculated (7). If the lower limit of the 95% CI of the OE ratio is greater than 1, the observed value is considered significantly higher than expected (Figure 2, case [a]). If the upper limit of the 95% CI of the OE ratio is lower than one, the observed value is considered significantly lower than expected (Figure 2, case [b]). If the 95% CI contains 1, then the observed and the expected numbers will not be considered significantly different (Figure 2, case [c]).

[figure not shown]
Figure 2. Observed to Expected (OE) Ratios and 95% Confidence Intervals (CIs)

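### For chronic, relapsing or gradual-onset events, the OE analysis sets reported cases, with worsening of old diagnoses not excluded and diagnoses at planned visits not solicited, against an expected count of new cases.

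*Protocol*

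**What the plan says.** **Expected count.** Protocol section 9.7 says the background rate "is the number of new cases occurring naturally in the population, expressed in person-time".

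**Observed count.** The same paragraph continues: "Expected numbers are then compared with the number of cases actually reported in vaccine recipients". Elsewhere in 9.7: "Counts of newly reported medically attended safety events of interest and counts of vaccinated participants will be summarized". Section 9.5 describes the numerator of the rate as "calculated as the number of participants experiencing the event after receiving a dose of the Pfizer-BioNTech COVID-19 mRNA vaccine". None of these sentences excludes a participant who already had the diagnosis.

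**Scope of the outcome.** Section 9.1 states: "This study will collect information on all reported occurrences of the medically attended safety events of interest". The Abstract limits these to events "for which the participant sought medical care during the study period". Section 9.4.2 collects medically attended events since the last follow-up. None of the three limits the care to unplanned care.

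**Questionnaire.** In Annex 3, section 18.1.3, the event questions open with "Have you received any non-routine (unplanned) medical care since your vaccination / last follow-up questionnaire". Only a yes leads on to the diagnosis list. The participant then classifies each event as a first diagnosis or under the option "I have been diagnosed with this condition in the past, but my symptoms changed or got worse". Both answers go on to the same list of safety events.

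**Provider form.** Section 18.1.5 asks the treating provider to confirm the treating role, dates, diagnosis, outcome and frailty, with a VAED assessment for severe COVID-19. It has no item on new onset versus recurrence.

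**The concern.** An OE ratio has a null value of 1 only if both counts use the same case definition and the same route of ascertainment. Here they differ in two ways.

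A relapse of a known disease adds to the observed count but has no counterpart in a rate of new cases, so the ratio is pushed up. Provider validation does not remove it: a relapse of true multiple sclerosis is correctly confirmed as multiple sclerosis.

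In the other direction, a new diagnosis made only at a scheduled appointment is not solicited. If the background source counts it, the ratio is pushed down.

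Table 2 contains events open to both errors without a hospitalised-only mark, for example multiple sclerosis, arthritis, fibromyalgia and autoimmune thyroiditis. Heart failure, coronary artery disease and arrhythmia carry that mark in the COVID-19 block but reappear without it in the Cardiac block, so the restriction is not uniform.

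The first secondary objective is at stake. Section 9.7 reads a lower 95% limit above 1 as a significant excess, so a mismatch of definitions could produce a signal or hide one.

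**Working it through.** **1. The plan's own figure.** 10,000 completers at 25% dropout: 10,000 / (1 − 0.25) = 13,333.3, rounded up to 13,334. This agrees with sections 9.2 and 9.5. The point does not depend on it, but it supplies the person-time below.

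**2. Expected OE with no vaccine effect.** Let f be the share of observed events that are flare-ups, and m the share of new diagnoses made only at planned care and not reported. Then OE = (1 − m) / (1 − f). The protocol gives neither share; 0% to 50% is an assumed range.

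| | 10% | 25% | 50% |
|---|---|---|---|
| f, with m = 0 | 1.11 | 1.33 | 2.00 |
| m, with f = 0 | 0.90 | 0.75 | 0.50 |

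The two errors cancel only when f = m, for example (1 − 0.25) / (1 − 0.25) = 1.00. Nothing in the protocol makes them equal, and they will differ by event.

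**3. The decision rule.** Take 10 new cases per 10,000 person-years, one of the rates in Table 4, and 10,000 completers × 2 years = 20,000 person-years. The expected count is 20. The exact Poisson lower limit is 19.4 at 29 observed cases and 20.2 at 30, so a signal needs at least 30.

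**4. False signals.** The observed count is Poisson with mean 20 / (1 − f), with no vaccine effect and m = 0.

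| f | Mean | P(at least 30) |
|---|---|---|
| 0 | 20.0 | 2.2% |
| 10% | 22.2 | 6.6% |
| 25% | 26.7 | 28% |

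**5. Missed signals.** With a true doubling and f = 0, the mean is 40 × (1 − m).

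| m | Mean | P(at least 30) |
|---|---|---|
| 0 | 40 | 95.7% |
| 10% | 36 | 86.2% |
| 25% | 30 | 52.4% |

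**6. Which step could remove flare-ups.** The baseline history records mostly broad groups, such as chronic neurological or rheumatological disorder, which may not identify a prior case of a specific event. The provider form does not ask. The item on first versus past diagnosis is the direct separator, and 9.7 does not mention it.

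**The case against.** *The numerator is a matter for the SAP.* The option on worsening is one half of a pair that separates old from new diagnoses, and an SAP that is not shown may restrict the OE numerator to new ones. A reader might infer that the protocol commits to counting flare-ups. It does not; it fails to exclude them while defining the expected side as new cases. That narrower statement stands. The wording of the opening question is different in kind, because no later analysis plan can recover events that were never asked about.

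*Planned-visit diagnoses are not lost.* This is right. The Abstract and section 9.1 allow participants to report at any time outside the schedule, and the opening question accepts general practitioner and hospital outpatient care if unplanned. A reader might infer that such diagnoses are omitted; the documents support only that they are not solicited.

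*Most events are unaffected.* A reader might infer that every OE ratio is invalid. The protocol does not support that: anaphylaxis, seizure, stroke or pulmonary embolus plausibly reach unplanned care and may be little affected. Which events are exposed is a judgement, and so is the assumption that the background databases count planned-visit diagnoses, since their case definitions are not given. Secondary analyses are also exploratory, and OE is run only where cases suffice. These points limit the reach of the problem but do not resolve it for chronic events.

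*Worsening may itself be a vaccine effect.* This is true, and it is a reason to report such events separately and not discard them. It also argues against restricting the SCRI analysis, which compares windows within cases and uses no background rate, so this mismatch does not arise there.

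**Conclusion.** The concern holds for chronic, relapsing or gradual-onset events without a uniform hospitalised-only restriction. As written, the OE comparison sets reported cases, prior diagnoses not excluded, against new cases. The scheduled questionnaire also solicits a narrower set of events than sections 9.1 and 9.4.2 define.

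The first mismatch pushes OE up. The second pushes it down where the background source includes planned-visit diagnoses. Size and net direction cannot be read from the protocol. The rise in false-signal probability from about 2% to about 7% to 28% is an illustration. It rests on 20 expected cases, an assumed flare-up share of 10% to 25%, no under-reporting and no vaccine effect. The issue should be corrected, but it does not undermine the OE analysis of acute events.

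**What to change.** 1. **Section 9.7 and provider form.** State that the OE numerator uses events flagged as a first diagnosis. Add a new-onset item to the form in 18.1.5. Tabulate worsening of prior conditions separately. Leave SCRI unrestricted, and show incidence rates both for all events and for first diagnoses.

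2. **Section 18.1.3.** Align the opening question with 9.4.2 by asking about any medical care, planned or unplanned, for a new diagnosis or for new or worsened symptoms. Record whether the care was planned, so that reports before and after the change of wording can be compared.

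**Cost.** The participant-level flag is already collected, so its use in the analysis is nearly free. The rest needs a protocol amendment, one added provider item, one reworded question and somewhat more reports to validate. Data collection was planned to start on 31 August 2021, so the new wording changes ascertainment during the study and should be documented as such.
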